9.2.2.2. Safety

- Incidence of treatment emergent adverse event (TEAE), adverse event of special interest (AESI) and serious adverse event (SAE); severity of adverse event will be assessed (based on NCI CTCAE 5.0);
- Incidence of adverse events resulting in dose adjustment of the study drug or termination of the study;
- Changes in each parameter like ECOG score, vital signs, electrocardiogram, left ventricular ejection fraction, dermatologic examination and laboratory indicators from baseline.

9.2.2.3. Pharmacokinetic characteristics

Descriptive statistics and summary of drug concentration at relevant time points will be carried out according to plasma concentration of DCC-2618 (ripretinib, ZL-2307). If necessary, pharmacokinetic data of this study will be included into population PK analysis with industrial standard software. Population PK report will be drafted independently and not taken as the appendix of the study report.

9.2.3. Exploratory endpoint

- KIT/PDGFRA mutation of tumor tissues at baseline and specific time points (e.g., resection of metastasis or progressive disease during the study).
- KIT/PDGFRA mutations and mutant allele frequency at baseline and the treatment effect of DCC-2618 (ripretinib, ZL-2307) on KIT/PDGFRA mutant allele frequency (MAF).

9.3. Analysis Population

The following populations will be used for analysis: all patients intent-to-treat (ITT) population, KIT exon 11 mutation intent-to-treat (Ex11 ITT) population, safety population, PK population, all patients per-protocol (PP) population and KIT exon 11 mutation per-protocol (Ex11 PP) population.

ITT population is defined as all randomized patients. Patients in the population will be analyzed according to treatment they will receive.

KIT exon 11 mutation intent-to-treat (Ex11 ITT) population is defined as all patients with KIT exon 11 mutation at randomization. Patients in the population will be analyzed according to

treatment they will receive.

Safety analysis population is defined as all subjects who were randomly assigned and received at least one dose of study drug. Safety population will be used for all safety analyses and treatment assignment will be based on the actually received initial study treatment.

PK population will include all randomized subjects who have received at least one dose of DCC-2618 (ripretinib, ZL-2307) and have at least a non-missing plasma PK concentration report of DCC-2618 (ripretinib, ZL-2307) and DP-5439.

PP population is defined as all patients in ITT population who have at least one tumor assessment after baseline, meet all inclusion criteria, don't violate any exclusion criteria and don't have any significant study protocol violation/deviation that are considered to influence the integrity of the study. Efficacy analysis in the PP population is supportive and the analysis in treatment groups will be based on the actually received treatment. Patients who violate the study protocol and excluded from the PP population will be identified and recorded before locking the database.

KIT exon 11 mutation per-protocol (Ex11 PP) population is defined as all patients in Ex11 ITT population who have at least one tumor assessment after baseline, meet all inclusion criteria, don't violate any exclusion criteria and don't have any significant study protocol violation/deviation that are considered to influence the integrity of the study. Efficacy analysis in the Ex11 PP population is supportive and the analysis in treatment groups will be based on the actually received treatment. Patients who violate the study protocol and excluded from the Ex11 PP population will be identified and recorded before locking the database.

Note: If a patient has exon 11 mutation with 1) exon 9 and/or PDGFRA mutation, the patient will be considered with exon 11 mutation at randomization. Mutation type of the patient will be defined according to a mutation with a higher MAF if the patient has mutation allele frequency (MAF) data; 2) other KIT exon mutation, the patient will be considered with exon 11 mutation at randomization.

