- 9. Use of strong or moderate inhibitors and/or inducers of cytochrome P450 (CYP) 3A4 within 14 days or 5 x the half-life (whichever is longer) prior to the first dose of study drug, including certain herbal medications (eg, St. John's Wort) and consumption of grapefruit or grapefruit juice within 14 days prior to the first dose of study drug. For CYP3A4 enzyme inhibition/induction-related drugs, please refer to the website of the Indiana University, School of Medicine

(http://medicine.iupui.edu/clinpharm/ddis/main-table/).

- 10. Use of known substrates or inhibitors of breast cancer resistance protein (BCRP) transporters within 14 days or 5 x the half-life (whichever is longer) prior to the first dose of study drug. For information of inhibitors and substrates, please refer to Food and Drug Administration (FDA) website: https://www.fda.gov/Drugs/DevelopmentApprovalProcess/DevelopmentRe sources/DrugInteractionsLabeling/ucm093664.htm.
- 11. Major surgeries (e.g. abdominal laparotomy) within 4 weeks of the first dose of study drug; all major surgical wounds must be healed and free of infection or dehiscence before the first dose of study drug.
- 12. Any other clinically significant comorbidities, such as uncontrolled pulmonary disease, active infection, or any other condition, which in the judgment of the investigator, could compromise compliance with the protocol, interfere with interpretation of the study results, or predispose the patient to safety risks.
- 13. Known human immunodeficiency virus or hepatitis C infection only if the patient is taking medications that are excluded per protocol, hepatitis B virus (HBV) DNA > 2000 IU/ml or $> 10^4$ copies/ml.
- 14. Female patients who are pregnant or lactating or who plan to become pregnant during the study treatment period.
- 15. Known hypersensitivity to any component of the study drug. Patients with Stevenson Johnson syndrome in previous TKI treatment need to be excluded.
- 16. Gastrointestinal abnormalities including but not limited to:
 - inability to take oral medication
 - malabsorption syndrome
 - Requiring intravenous nutrition

17. Any active hemorrhages, excluding hemorrhoids or gum bleeding.

Study drug

Drug of the test group: DCC-2618 (Ripretinib, ZL-2307)

Dosage: 150 mg QD continuous administration, 6 weeks (42 days) for a cycle.

Administration route: oral

Drug of the control group: Sunitinib

Dosage form: capsule

Dosage Form: Tablet

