- In terms of collected archived tumor tissue samples, the central laboratory will analyze tumor tissues to identify molecular mutation of KIT or PDGFRA. Formalin-fixed paraffin-embedded tissue blocks (preferred) or unstained FFPE slices are required. If the archived tumor samples are unusable or inapplicable, new fresh tumor samples must be collected.
- Tumor tissue samples can be collected at EOT visit from all patients (optional) and/or from patients who are receiving medical procedures, including resection of metastasis in the study, or from patients who have progressed (if the patient agrees). These samples will be used for further molecular test of cancer during receiving the study drug.
- 20. Radiographic images must be done within 28 days before the first dose of the study drug. Radiographic examination prior to informed consent can be used for screening evaluation as long as the examination is performed within 28 days prior to the first dose of the study drug. Pelvic, abdominal and chest enhanced CT scan will be carried out at screening. During the study, pelvic and abdominal enhanced CT scan will be carried out on Day 1 of Cycles 2 7 and Day 1 of subsequent every odd cycle (such as Cycles 9, 11 and 13). If patients have lung metastases or symptoms of lung metastases at screening and during the study, chest CT enhanced scan should be performed (at the investigator's discretion). Radiographic images can be performed within the corresponding study visit ±

7 days. After C7D1, based on the investigator's assessment, any initially indicated partial or complete response should be confirmed ≥ 4 weeks after the start of response. MRI scans of the abdomen/pelvis and CT scan without contrast of the chest can be used for patients who are allergic to radiographic contrast media or at the Investigator's discretion based on the best interest of the patient after discussion with the Sponsor. For each patient, the same evaluation technology should be adopted during the whole study, and the evaluation technology could not be changed unless the investigator's consideration of safety risk. Ultrasound scan should not replace CT scan.

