9.5.5. Efficacy analysis

9.5.5.1. Primary endpoint: progression-free survival

The primary endpoint PFS is defined as the time interval from randomization to the earliest documented evidence of progressive disease based on assessment of the independent radiology review or death due to any causes. PFS analysis in the ITT population will be stratified by the randomization stratification factors (KIT exon 11 mutation; KIT exon 9 mutation; other (KIT/PDGFRA WT or other KIT [lacking exon 9 or 11]/PDGFRA mutation). Survival curve of different treatment groups will be plotted with KM method and the median progression-free survival (mPFS) and its 95% CI of different groups will be calculated. Under a two-sided significance level of 0.05, stratified log-rank test will be adopted to compare difference in survival curve between the two groups. Point estimate of hazard ratio will be obtained by stratified Cox regression model and relevant 95% CI will be calculated with Wald method. Randomization stratification factor is stratification factor and treatment factor is the covariant.

Rules of defining PFS events and censoring PFS will be elaborated in the statistical analysis plan (SAP). Sensitivity analysis for PFS will be specified in the SAP.

ITT population will be used as the primary analysis population in this analysis while the PP

population as supportive analysis population. Sensitivity analysis of progression-free survival will be performed, which will be further described in SAP.

Zai Lab

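### The PP and Ex11 PP sets require a post-baseline tumour assessment, so a patient who dies before any scan is a PFS event in ITT but is dropped from the supportive PFS analysis

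*Combined protocol and SAP*

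**What the plan says.** **Analysis sets (section 9.3).** The "PP population is defined as all patients in ITT population who have at least one tumor assessment after baseline". Eligibility and the absence of significant deviations are further conditions. The Ex11 PP set repeats the rule: it "is defined as all patients in Ex11 ITT population who have at least one tumor assessment after baseline".

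**Role of PP.** "Efficacy analysis in the PP population is supportive" (section 9.3). For PFS, "ITT population will be used as the primary analysis population in this analysis" (section 9.5.5.1). The same split between ITT and PP is stated for ORR in section 9.5.5.2.1.

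**Endpoint (section 9.5.5.1).** PFS runs from randomization to the "earliest documented evidence of progressive disease based on assessment of the independent radiology review or death due to any causes".

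**Scan timing.** Footnote 20 of Table 1 says "pelvic and abdominal enhanced CT scan will be carried out on Day 1 of Cycles" 2 to 7, within 7 days either side. The synopsis gives the ripretinib regimen as "150 mg QD continuous administration, 6 weeks (42 days) for a cycle", and the sunitinib cycle is also 42 days. The first scheduled post-baseline scan is therefore at about week 6.

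**ORR (section 9.5.5.2.1).** Unknown or missing responses are treated as non-response and stay in the denominator.

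**The concern.** Eligibility and protocol deviations describe how well the trial was carried out in a patient. Having a post-baseline scan is different: it depends on what happens after randomization, including on survival. A patient who dies before being scanned has failed on the primary endpoint, and the PP rule removes that patient because of the failure.

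The PP analysis is there to show whether the ITT result holds among patients treated as planned. If the two differ, the reader will look to adherence for the reason, when it may be a handful of early deaths. Agreement can be produced in the same way. For ORR, the population rule also overrides the plan's own missing-data rule, because patients who are not in the set cannot be counted as non-responders in it.

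**Working it through.** **1. The plan's own figures.** The consistency threshold keeps half the effect: 1 − 0.5 × (1 − 0.667) = 0.833. With 1:1 allocation and Var(ln HR) = 4/d, the chance of an observed HR at or below the threshold is Φ[ln(threshold/HR) × √(d/4)].

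- All patients: ln(0.833/0.667) × √(58/4) = 0.222 × 3.808 = 0.846, giving 80.1% (stated: 80%).
- Exon 11: ln(0.778/0.556) × √(26/4) = 0.336 × 2.550 = 0.857, giving 80.4% (stated: 80%).
- Expected events from 98 patients, with exponential PFS, medians of 9 and 6 months, uniform accrual over 7 months, 7 months of further follow-up and 5% annual drop-out: 59.8 (stated: 58).

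The design figures reproduce, and none of them uses the PP definition.

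**2. Who is lost.**

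| Patient with no progression on a scheduled scan yet | PFS in ITT | In PP? |
|---|---|---|
| Dies before any post-baseline scan | Event | No |
| Worsens clinically and has an unscheduled scan | By independent review | Yes, if otherwise eligible |
| Worsens, is never scanned, does not die | No event under section 9.5.5.1 | No |

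Only the first row is a PFS event that PP discards. For ORR, the first and third rows are both non-responders in ITT and both missing from PP.

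**3. A ceiling.** 42 days is 42/30.44 = 1.38 months. Under the planning medians, the share with a PFS event by then is 1 − exp(−ln 2 × 1.38/9) = 10.1% for ripretinib and 1 − exp(−ln 2 × 1.38/6) = 14.7% for sunitinib, or 49 × 0.101 + 49 × 0.147 ≈ 4.9 + 7.2 ≈ 12 of 98. Most of these would be progressions seen on a scan, and those patients stay in PP. Deaths without a scan are an unknown part of the 12.

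**4. Effect on the HR, by assumption.** The documents give no rate of unscanned early deaths, so 0 to 4 per arm were assumed. In the simulation (4,000 trials per row, 49 per arm, unstratified Cox model) the named number of patients die at a uniform time before week 6 and all others follow the planning assumptions.

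| Early unscanned deaths, ripretinib/sunitinib | HR if kept | HR if removed | Chance of HR ≤ 0.833, kept → removed |
|---|---|---|---|
| 0/0 | 0.66 | 0.66 | 81% → 81% |
| 2/2 | 0.69 | 0.67 | 78% → 79% |
| 3/1 | 0.73 | 0.67 | 71% → 80% |
| 1/3 | 0.64 | 0.67 | 85% → 80% |
| 4/0 | 0.78 | 0.67 | 61% → 80% |
| 0/4 | 0.60 | 0.66 | 91% → 82% |

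The removed column stays near 0.67 by construction; the information is in the gap between the two HR columns. The last column shows only how far ITT and PP can drift apart on the plan's own yardstick, because the plan does not apply that rule to PP.

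**5. Exon 11.** The set is smaller, so each death counts for more. With an assumed 22 patients per arm, one unscanned ripretinib death gives about 0.61 kept and 0.56 removed; two give about 0.68 and 0.56. A repeat run agreed to within about 0.02.

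**6. ORR.** Removing k non-responders from an arm of 49 multiplies its ORR by 49/(49 − k). Taking the second-line phase 1 ORR of 19.4% (section 1.3.2.3) as an illustration, k = 1, 2 or 3 gives 19.8%, 20.2% or 20.7%. Within an arm the change is never downward; the difference between arms can move either way.

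**The case against.** The strongest reply is that nothing decisive rests on PP. ITT keeps every randomized patient, the primary analysis at 58 events is an ITT analysis, and PP is labelled supportive. Requiring a post-baseline efficacy assessment is a familiar convention, and it is stated openly. All of that stands, and it is why the point is minor.

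A second reply is that PFS event, censoring and sensitivity rules are left to a SAP whose text is not among the documents reviewed. That SAP might make an exception for early deaths, and this cannot be checked. Censoring rules alone would not help, however, because they act only on patients who are already in the set.

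Three stronger readings are tempting and are not supported:

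- **Patients who deteriorate before week 6 are also lost as events.** Clinical deterioration is not a PFS event under section 9.5.5.1. Section 6.10.1 calls for imaging and independent review when the investigator concludes progression from clinical worsening, and section 6.6 allows unscheduled efficacy assessments at any time. Any such scan keeps the patient in PP.
- **The consistency verdict is at risk of a false pass.** No section applies the 0.833 rule to PP.
- **The rule favours ripretinib.** The direction depends on which arm has more unscanned deaths: removal lowers the HR in the 3/1 case and raises it in the 1/3 case.

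**Conclusion.** The point holds for deaths before any post-baseline scan. They are PFS events in ITT and are excluded from the supportive PP and Ex11 PP analyses by a condition that depends on the outcome. It also holds for the PP ORR denominator, where it bypasses the missing-response rule.

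The size cannot be derived from the documents. Under the assumed counts, the all-patient HR shifts by about 0.02 when the deaths are balanced (2/2), by 0.03 to 0.06 when they split 1/3 or 3/1, and by up to about 0.11 at 4/0. These values rest on exponential PFS at the planning medians and on the assumed death counts. If no patient dies unscanned, the PFS analysis loses no event. The primary result, the event trigger and the consistency conclusion are unchanged in every case. This is a minor improvement, worth making because it is nearly free.

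**What to change.** In both definitions in section 9.3, do one of the following:

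1. Delete the post-baseline-assessment condition and define PP and Ex11 PP by eligibility and significant protocol deviations only. This is the cleaner option, because it also lets the ORR missing-response rule work in PP.
2. Keep the condition, and state that death before the first post-baseline assessment satisfies it. This repairs PFS. For ORR it restores the deaths, but not living patients who were never scanned.

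Widening the condition to admit unscanned patients with documented clinical progression would not restore PFS failures: under section 9.5.5.1 they have no event unless they die, so they would enter only as censored observations.

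The cost is one phrase in two definitions, with no new data. PP will contain a few patients without a scan, who count as non-responders for ORR and, if alive with no event, are censored for PFS. The change should be made before PP exclusions are identified ahead of database lock, and the SAP should carry the same wording.

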9.4. Processing procedures of missing data, unused data and false data

Calculation of interpolating or missing date is shown in Table 166. Interpolate AE end date to calculate the duration of AE.

Table 166: Calculation of some or missing date

Variables	Missing Day	Missing date and month	Missing date, month and year
Date of the last treatment/initial diagnosis	Assigned 1 day	Please assign January 1 if before the date of informed consent, or else use the date of informed consent	O \
AEs/Starting date	Assign the first day of the	Assign January 1, unless	Assign the date of the

	month, unless the first dose	the first dose of the study	first dose of the study
	of the study drug is given in	drug is given this year.	drug.
	this month.	Or else, assign the date of	
	Or else, assign the date of	the first dose of the study	
	the first dose of the study	drug or end date of AE (if	
	drug or end date of AE (if	not missing), whichever	
	not missing), whichever	occurs first.	
	occurs first.		
The end date of	Assign the last day of this	Assign December 31 or	If the event continues,
adverse event	month or study end date,	study end date,	end date will be left
	whichever occurs first.	whichever occurs first.	blank. Otherwise, study
			end date was to be
			assigned.

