Random assignment ²²		X								
Evaluate AE, collect information of concomitant medications/other treatments, collect information of new anti-tumor therapies									х	
Collect new information of anti-tumor therapy and OS data										X

CT = computerised tomography; ECG = electrocardiogram; ECOG = Eastern Cooperative Oncology Group; EOT = end of treatment; MRI = magnetic resonance imaging; PD = pharmacodynamic; PK = pharmacokinetic; PS = performance status

^{*:} Examination with * doesn't need to be repeated on C1D1 if examination at screening is performed within 7 days prior to the first dose of the study drug.

- Unless otherwise specified, all assessments must be carried out prior to administration and in the predetermined window of visit. Cycle is not influenced by suspension or delay of treatment with the study drug. Additional unscheduled safety or efficacy assessment can be carried out at any time with clinical indications to confirm the correlation between the specific findings and the study drug and/or duration of event. At unscheduled visits, if necessary, distribution and/or recovery of the study drug can be carried out.
- ^{2.} Screening must be done within 28 days before the first dose of the study drug.
- All patients will be followed up until withdrawal of consent or death for any reason. After safety follow-up visit, patients will be contacted once every 2 months (± 10 days) to collect new information of anti-tumor therapy and OS data.
- 4. Any medications or other therapies taken within 30 days prior to signing the informed consent form and prior to the first dose of the study drug.
- A serum pregnancy test will be performed, at screening, for females of child-bearing potential. If serum pregnancy test at screening is performed within 7 days prior to the first dose of the study drug, urine pregnancy test is not required on C1D1. Urine pregnancy test will be carried out at visit of Day 1 of every subsequent cycle and EOT visit.

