7.9. Adverse Events of Special Interest (AESIs)

An AESI is an AE (serious or nonserious) of scientific and medical concern specific to study drug, for which ongoing monitoring and immediate notification by the Investigator to the Sponsor is required. Such AEs may require further investigation to characterize and understand them. AESIs may be added or removed during a study by a protocol amendment.

The following AEs are considered AESIs:

- Squamous cell carcinoma of skin
- Actinic keratosis
- Keratoacanthoma

7.10. **Adverse Events Reporting Period**

The AE (including SAEs and AESIs) reporting period begins from the time that the patient provides informed consent through and including 30 days after the last dose of the study drug, or until a new anti-tumor therapy is initated, which occurs first. For any SAEs or AESIs occurring after this reporting period, it will be reported only when a causal relationship between the SAEs or AESIs and study product is suspected by the study drug.

7.11. Adverse Event, Serious Adverse Event, and Adverse Event of Special Interest Reporting Requirements

Each patient must be carefully monitored for the development of any AEs. This information must be obtained in the form of non-leading questions (e.g. "How are you feeling?") and from signs and symptoms detected during each examination, observations of study personnel, and spontaneous reports from patients. All AEs (serious and non-serious) spontaneously reported by the patient and/or in response to an open question from study personnel or revealed by observation, physical examination or other diagnostic procedures must be recorded.

When possible, signs and symptoms indicating a common underlying pathology must be noted as 1 comprehensive event. Accompanying signs or symptoms (e.g. abnormal laboratory values) must not be reported as additional AEs. If a diagnosis is unknown, one or more symptoms may be reported as separate AEs. If an underlying diagnosis is subsequently determined for the reported symptom(s), then the reported symptom(s) term(s) must be revised to be "attributed" or "due" to the diagnosis.

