9.5.6.1. AEs

AEs in the safety population will be summarized with the number of events and proportion of patients according to system organ class (SOC) and preferred term. All tables will only include TEAE. "Treatment emergent" is defined as any AEs occurring during the first dose of the investigational drug and up to 30 days after the last dose of the investigational drug. However, the listing will include all AEs collected.

Toxicity grade of AE will be classified with NCI-CTCAE V5.0 (See Table 12). If a patient has the same SOC or preferred term evet for several times, only the most severe event will be summarized in the tables for that SOC and preferred term. AEs grade ≥ 3 will be summarized. Missing toxicity grade will not be imputed.

SAEs, AEs and AESIs that lead to dose reduction or discontinuation and AEs will be also analyzed.

Formal hypothesis test of incidence of AE will not be performed.

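### Table 16 gives an AE with a fully missing start date the first-dose date without the end-date limit used in its other two columns, so onset can be imputed after a known end date

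*Combined protocol and SAP*

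**What the plan says.** All references are to the combined protocol and SAP.

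- **Section 9.4, Table 16 (printed as Table 166), AE start-date row.** There are three rules.
  - *Day missing:* the first of the month, unless first dose falls in that month. In that case it is the first-dose date or the AE end date if recorded, whichever is earlier. The clause contains the words "drug or end date of AE (if".
  - *Day and month missing:* 1 January, unless first dose falls in that year. In that case the same earlier-of rule applies.
  - *Day, month and year missing:* the cell opens "Assign the date of the", continues "first dose of the study" and closes with the word drug and a full stop. It does not mention the AE end date.
- **Section 9.4, opening text.** The stated purpose of imputing the end date is duration: "Interpolate AE end date to calculate the duration of AE". No formula is given.
- **Section 7.10.** The AE "reporting period begins from the time that the patient provides informed consent".
- **Table 1, footnote 2.** "Screening must be done within 28 days before the first dose of the study drug".
- **Section 9.5.6.1.** Treatment emergent "is defined as any AEs occurring during the first dose of the investigational drug and up to 30 days after the last dose", and "All tables will only include TEAE". The listing is to carry every AE collected.

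**The concern.** Assigning first dose to an AE of unknown onset is a usual conservative choice. It stops being sensible when a recorded end date shows that the event was over before treatment began. The first two columns of Table 16 allow for this and the third does not. The treatment of an event already known to be pre-dose therefore depends on how much of its start date is missing.

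Two things are at stake. The first is internal consistency: an onset later than its own end date is impossible and would fail a routine data check. The second is the content of the AE tables, which are restricted to treatment-emergent events. TEAE incidence is a secondary safety endpoint (Section 9.2.2.2), and comparing the two safety profiles is a secondary objective (Section 2.2). If the treatment-emergent flag is set from the imputed start date, a screening event could be tabulated as treatment-emergent.

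**Working it through.** The plan gives no figure to reproduce, so the check applies the three rules as written to one hypothetical patient.

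**Inputs**
- First dose: 29 March 2021 (arbitrary, for illustration).
- AE end date: known, at 28, 14 or 1 day before first dose, on the day of first dose, or 5 days after. The 28-day limit comes from Table 1, footnote 2, and assumes that consent falls inside the screening window, where Table 1 places it.
- In the first two columns, first dose falls in the month or year recorded for the AE start. This is the only branch that assigns first dose, so it is the right comparison.

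**Rules**
- First two columns: start = min(first dose, AE end date).
- Third column as written: start = first dose.
- Duration: no formula is given, so both usual forms are shown, D0 = end - start and D1 = end - start + 1.

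**Results**

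| AE end date | Relative to first dose | Start, columns 1 and 2 | D0 / D1 | Start, column 3 | D0 / D1 |
|---|---|---|---|---|---|
| 1 March | -28 days | 1 March | 0 / 1 | 29 March | -28 / -27 |
| 15 March | -14 days | 15 March | 0 / 1 | 29 March | -14 / -13 |
| 28 March | -1 day | 28 March | 0 / 1 | 29 March | -1 / 0 |
| 29 March | 0 days | 29 March | 0 / 1 | 29 March | 0 / 1 |
| 3 April | +5 days | 29 March | 5 / 6 | 29 March | 5 / 6 |

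For example, in the second row of column 3, D0 = 15 - 29 = -14 and D1 = -14 + 1 = -13.

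**Treatment-emergent status.** Suppose the flag is defined as imputed start on or after first dose. The three pre-dose events are then treatment-emergent under column 3 and not under columns 1 and 2. That definition is an assumption, because Section 9.5.6.1 speaks of AEs occurring in the window and does not say which date decides.

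**With the limit added to column 3.** Start = min(first dose, AE end date) where an end date is recorded. The three pre-dose events then start on their end dates, with D0 = 0 and D1 = 1, and fall outside the treatment-emergent window. Events ending on or after first dose do not change. If the end date is also missing, first dose is still assigned.

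**The case against.** The strongest reply is that almost no event will meet the conditions. The AE must have begun after consent, within a screening window of at most 28 days. Day, month and year of onset must all be unknown, while the end date is known to precede dosing. With onset bounded by consent and the end date, the year can nearly always be inferred, which moves the event to a column that has the limit. Monitors check the eCRF against source (Section 10.1), and the investigator answers for its accuracy (Section 11.1). In about 98 patients the count may well be zero. This stands and fixes the point as minor, but it does not make the rule right.

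A reader might infer three stronger things that the documents do not support:

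- *Every such AE becomes a false TEAE.* Section 9.5.6.1 does not say that the flag rests on the imputed start date alone. A programmer who also used the end date would exclude the event.
- *Pre-treatment events would be reported as drug toxicity.* Treatment-emergent is a category of timing. Relationship to study drug is judged separately by the investigator (Section 7.3), and Table 16 does not alter it.
- *Negative durations would distort a planned result.* Section 9.4 says that duration is calculated, but Section 9.5.6.1 specifies no summary of it. Under D1, an event that ended the day before dosing has duration 0, not a negative value.

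Two further replies carry less weight. In the text as read, the third-column cell of the row above is garbled, so lost text has to be considered. The AE start-date cell, however, is a complete sentence with a full stop. A separate SAP might add a rule, but Section 9.5.5.1 defers PFS event, censoring and sensitivity rules to it, whereas Section 9.4 defers nothing. No other text supplied overrides Table 16.

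**Conclusion.** Wrong as written, minor. For a fully missing start date and a recorded end date before first dose, Table 16 places onset after the end of the event. This follows from the rule itself and needs no further assumption.

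The size of the error depends on convention: a derived duration of -28 to -1 days as end minus start, or -27 to 0 days with one day added. The range assumes consent no more than 28 days before first dose. Miscounting as treatment-emergent is possible rather than certain, since it depends on a flag definition that the documents leave open. How many events are affected cannot be worked out from the documents, but it should be very few. The rule is the same in both arms, and neither the primary PFS endpoint nor the HR consistency criteria are affected.

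**What to change.** In the third column of the AE start-date row of Table 16, keep the first-dose date as the default and add the limit that the other two columns already carry: where an AE end date is recorded, use the earlier of that date and the date of first dose. The cost is one clause, with no new data and no change to any other row. It is best done before the AE derivations are programmed.
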